Figure 1 Summary of mechanisms by which tobacco smoke constituents cause an acute cardiovascular event.

to CV events in people with pre-existing CVD, including sudden death due to arrhythmia. SNS stimulation also contributes to a more atherogenic lipid profile and insulin resistance and diabetes, which are important CVD risk factors. Depending on device and use conditions, e-cigarettes produce nanoparticles consisting of metals, metal oxides, and other

compounds. Epidemiologic studies have long linked exposure to particles in ambient air to increased risk of CVD, cancer, and respiratory diseases.

We propose to measure biomarkers of exposure to potential CV toxicants (acrolein, nicotine, and CO). We will also measure biomarkers of relevant pathogenesis mechanisms related to acute CVD (oxidant injury, inflammation, platelet activation, endothelial dysfunction and SNS stimulation; SNS stimulation is measured as increased heart rate and blood pressure and urine catecholamines). Specific biomarkers with citations are summarized in **Table 3**. These biomarkers were selected since they have been shown to change rapidly after smoking, so we can assess short-term effects, and are known to be correlated with CVD risk. Our studies of different e-cigarette power and HNB products will include all of the biomarkers presented in **Table 3**. Since e-liquid pH is expected to influence primarily nicotine exposure and pharmacokinetics, the e-liquid pH study will focus on the effects of nicotine exposure and pharmacokinetics on hemodynamic parameters and not on the other CVD biomarkers.

Table 3: Cardiovascular Risk Biomarkers	
Function	Biomarkers
Sympathetic nervous system stimulation	Heart Rate Urinary catecholamines
Oxidative stress	Urinary F2-isoprostanate
Platelet activation / Thrombosis	Urinary 11-dehydro-thromboxane B2 (11-dTXB2)
Endothelial dysfunction	Plasma Vascular Endothelial Growth Factor (VEGF)
	Plasma Intracellular Adhesion Molecule-1 (ICAM-1)
Inflammation	Plasma interleukin 6 (IL-6)

E-cigarette Power is related to Nicotine Delivery and Toxicant Generation

E-cigarette electrical power (P), which is a function of battery voltage (V) and atomizer (coil) resistance (R) ($P = V^2/R$), may be one of the most important determinants of e-cigarette health effects. The heat supplied by the atomizer to raise the temperature of the e-liquid is a product of electrical power and length of time electricity is applied to the atomizer. The temperature of the heating e-liquid influences nicotine delivery, the type and amount of chemicals generated in the aerosol, and possibly aerosol particle size. In one study, the average power used by users of 2nd generation (pen-shaped) e-cigarettes and 3rd generation (variable voltage or wattage) e-cigarettes ranged from 9 to 76 W, with some individuals using as much as 160 W. Users of high-powered e-cigarettes typically use low nicotine content e-liquids but have similar or higher plasma nicotine levels than users of less powerful devices who use high nicotine content e-liquids. This is indicative of the large amounts of aerosol delivered to users of high-powered e-cigarettes and raises concerns about exposure to toxicants and contaminants in e-liquids. Further, propylene glycol (PG), vegetable glycerin (VG), and flavorants thermally decompose to chemicals such as formaldehyde and acrolein and reactive oxygen species in a temperature-dependent manner. Elevated biomarkers of acrolein exposure have not been reported in e-cigarette users. This is most likely because studies have not characterized acrolein exposure in users of high-powered e-cigarettes.

1 INTRODUCTION AND STUDY DESIGN

1.1 RESEARCH QUESTION

What are the effects of electronic cigarette device power?

1.2 SPECIFIC AIMS

1.2.1 Specific Aim #1

Determine the impact of e-cigarette device power on nicotine pharmacology, systemic exposure to toxic volatile organic compounds (VOCs), and short-term cardiovascular effects.

Hypothesis 1a: Systemic nicotine exposure and subjective measures of sensation in the throat, reward, and satisfaction will increase with increasing power.

Hypothesis 1b: Mercapturic acid metabolites of VOCs, particularly acrolein, will increase with e-cigarette power.

Hypothesis 1c: CV effects increase with higher power, and are manifested as changes in hemodynamic parameters, hormonal release, and biomarkers of endothelial function, platelet activation, inflammation, and oxidative stress.

2 STUDY DESIGN

2.1 DESIGN SUMMARY

This is a single-site, randomized, crossover study of experienced adult e-cigarette users to assess nicotine exposure, toxicant exposure, and the short-term CV effects of e-cigarette power. Three power levels will be assessed on all participants: 10, 15, and 20 watts.

2.2 STUDY TIMELINE

- Preparation for this study began 06/23/2017
- Application submitted to the IRB: 11/27/2017
- Approval date: 01/22/2019
- Expiration date: 01/16/2020
- Estimated start date: 02/15/2019
- Estimated end date: 12/15/2021

2.3 ELIGIBILITY

Potential participants will express interest in participation by filling out the secure REDCap survey hyperlink from advertisements, the UCSF Tobacco Research websites (e.g., Facebook), or by emailing the UCSF Tobacco Research Center email address. Participants will be contacted to take part in a confidential email screening to determine if they are eligible to come in for an in-person screening visit. If the participants are eligible for the study, they may choose to be e-consented or come in for an in-person screening visit. If the participants choose to be e-consented, a REDCap screening packet will be sent to them and it must be completed within 24 hours prior to

the in-person screening visit. At the in-person screening visit, participants will fill out case report forms (TC & EC use, medical history, etc.), the Clinical Research Coordinator (CRC) will take physiological measurements (blood pressure, height, weight, expired CO, etc.), and the participants will provide sample collections (urine and saliva). The participant's study chart will be reviewed by the Study Physician in order to determine study eligibility.

All individuals interested in participating and who meet the inclusion/exclusion criteria will be invited to be part of the study. Inclusion criteria are described below.

2.3.1 Inclusion Criteria

- Healthy on the basis of medical history and limited physical examination.
 - Heart rate < 105 BPM*
 - Systolic Blood Pressure < 160 and > 90*
 - Diastolic Blood Pressure < 100 and > 50*
 - Body Mass Index \leq 38.0 (at investigator's discretion for higher BMI if no other concurrent health issues)

**considered out of range if both machine and manual readings are above/below these thresholds*

- Use e-cigarettes on at least 15 days in the past 30 for at least 3 months
- Smoke 10 or fewer cigarettes per day in the last 30 days
- Willing to use a mod e-cigarette
- Willing to abstain from tobacco product use for 48 hours before each study visit
- Age: \geq 21 years old and \leq 70 years old
- Using e-liquid > 0 mg/ml nicotine
- Saliva cotinine of ≥ 30 ng/ml or NicAlert=6 (in cases where lab turn around time will delay study procedures)

2.3.2 Exclusion Criteria

- Medical
 - Seizures
 - Cancer
 - Hepatitis B or C or Liver disease
 - Oral thrush
 - Heart disease
 - Glaucoma
 - Kidney disease or urinary retention
 - Diabetes
 - High blood pressure
 - History of stroke
 - An ulcer in the past year
 - Thyroid disease (okay if controlled with medication)
 - Active use of an inhaler for asthma or COPD
- Psychiatric conditions
 - Current or past schizophrenia, and/or current or past bipolar disorder
 - Major depression, current or within the past year

- Major personality disorder
- Participants with current or past minor or moderate depression and/or anxiety disorders will be reviewed by the study physician and considered for inclusion
- History of psychiatric hospitalizations are not exclusionary, but study participation will be determined as per study physician's approval
- Recent onset or change in cough, fever and/or abdominal symptoms (vomiting or pain) in the past two weeks. (*If yes, participant can re-screen when symptoms resolve*).
- Drug/Alcohol Dependence
 - Alcohol or illicit drug dependence within the past 12 months (currently in treatment) with the exception of those who have recently completed an alcohol/drug treatment program
 - Positive toxicology test at the screening visit (THC & prescribed medications okay)
 - Opioid replacement therapy (including methadone, buprenorphine, or other)
- Positive urine cannabis is not exclusionary but participant must report use of cannabis and agree to abstain from cannabis use for the duration of the study
- Psychiatric medications
 - Current regular use of any psychiatric medications with the exception of SSRIs and SNRIs and current evaluation by the study physician that the participant is otherwise healthy, stable, and able to participate.
- Medications
 - Use of medications that are inducers of nicotine metabolizing enzyme CYP2A6 (Example: rifampicin, carbamazepine, phenobarbital, and other anticonvulsant drugs).
 - Concurrent use of nicotine-containing medications
 - Any stimulant medications (example: Adderall) generally given for ADHD treatment
 - Use of sympatholytic medications for cardiovascular conditions including hypertension (Example: beta and alpha-blockers)
- Other/Misc. Chronic Health Conditions
 - Fainting (within the last 30 days)
 - Other "life threatening illnesses" as per study physician's discretion
- Pregnancy
 - Pregnancy (self-reported and urine pregnancy test)
 - Breastfeeding (determined by self-report)
- Concurrent participation in another clinical trial
- Inability to communicate in English
- Planning to quit vaping within the next 60 days
- Uncomfortable with getting blood drawn

2.3.3 Eligibility Determination

After completion of in-person screening procedures, the CRC will complete an Eligibility Checklist which lists all inclusion/exclusion criteria and the participant's status based on responses in the case report forms. The Project

Manager and CRC will review the Eligibility Checklist after the saliva cotinine results are available.

The Project Manager and CRC will refer to the Study Physician or Principle Investigator if the participant:

- Currently takes any medications on schedule or as needed
- Has current or past depression and/or anxiety disorders
- Has any psychiatric hospitalizations in medical history

The Study Physician will review the information and sign off on the Eligibility Checklist or indicate that the participant is ineligible. If none of the above conditions are present, the CRC and Project Manager will sign off on Eligibility Checklist without Study Physician review.

The participant will be notified of eligibility via phone or email after this review.

2.3.4 Reassessment of Eligibility

Eligibility may need to be reassessed if the following conditions occur: the orientation visit is out of window (e.g. 90 days past from screening visit), and/or 30 days have passed since the time of the screening visit.

2.3.4.a Outside Orientation Visit Window

If the participant is outside of their orientation visit window of 90 days, the screening visit will be repeated. The original screening visit data will remain in the study chart, however it will not be used for analysis. The participant will repeat all visit procedures, forms, and provide a saliva sample to be re-sent for analysis.

2.3.4.b 30 Days Past Screening Visit

If 30 days have passed since the screening visit, in order to ensure that no significant changes have occurred in a participant's current medical status and smoking/vaping habits, the CRC will review some eligibility items. This will occur if the participant is more than 30 days, but less than 90 days outside of their screening visit window. The CRC will ask the following over the phone:

- if there are any new medications
- if they have seen a physician for any medical/psychological reason
- if they are still using their e-cigarettes as indicated at the in-person screening visit

If any significant changes have occurred, the CRC and Project Manager will meet to discuss and complete another Eligibility Checklist based on current participant responses.

2.4 IDs & Assignment

2.4.1 Study IDs

Participants who are eligible for an in-person screening visit will be assigned a unique Study ID upon consent to participate in the study. This Study ID will begin with the “####” to refer to the CTSI-5B study number, which is how the study is referred to at the research ward. These numbers (to be determined after in-service meeting with CTSI-5B) will be followed sequentially starting from 001. For example, the first participant enrolled will have a Study ID of ####001.

The Screening Visit Log will keep track the REDCap IDs, and Study IDs (if consented).

Password for TCORS-1 Participant Log: **7775enr**

2.4.2 Randomization

Participants will be assigned to begin procedures starting with one of three possible power levels using a Latin square design.

1) 10 Watts

OR

2) 15 Watts

OR

3) 20 Watts

Orientation # (N= 21)	Sequence	Study ARM 1	Study ARM 2	Study ARM 3
1	1	10W	15W	20W
2	2	15W	20W	10W
3	3	20W	10W	15W
4	4	20W	15W	10W
5	5	10W	20W	15W
6	6	15W	10W	20W
7	1	10W	15W	20W
8	2	15W	20W	10W
9	3	20W	10W	15W
10	4	20W	15W	10W
11	5	10W	20W	15W
12	6	15W	10W	20W
13	1	10W	15W	20W
14	2	15W	20W	10W
15	3	20W	10W	15W
16	4	20W	15W	10W
17	5	10W	20W	15W
18	6	15W	10W	20W
19	1	10W	15W	20W
20	2	15W	20W	10W
21	3	20W	10W	15W
22	4	20W	15W	10W
23	5	10W	20W	15W
24	6	15W	10W	20W

The participant will not be considered for assignment until it has been verified that he/she is eligible and the Eligibility Checklist has been signed. The experimental design includes a counter-balanced randomized treatment order to complete replication with total sample sizes of 21 or 24 (complete Blocks of n= 3). At the orientation visit, the participant will be assigned their treatment sequence from the above randomization schedule. In cases where a block will be incomplete because a participant has dropped out or been lost to follow up, their orientation assignment can be reused.

The final order assignment will take place at the orientation visit when the participant is physically present at the UCSF Tobacco Research Center. The CRC will refer to the "Assignment Tracking Log," input the participant's initials, product assignment, and date he/she is assigned to that condition. Assignment does not necessarily reflect the sequence of the participant's consent in the study, but rather when he/she is booked for the start of orientation. That time course will vary based upon participant, CRC and CTSI availability.

If a participant drops out or is lost to follow-up (LTFU) during the study, he/she will not be replaced. The assignment schedule will continue as assigned, and the PI can decide to enroll additional participants to compensate for non-completers.

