5.3.1 Product Assignment

Three e-cigarette device power levels will be assigned to all participants: low, medium, and high battery levels (10, 15, 20 Watts). The order of the assignment will be randomized, single-blinded.

E-liquid Selection: We will obtain the e-liquid from AVAIL, a leading premium e-liquid manufacturer and retail business which works with academic centers to provide research grade products that come with certificates of analysis confirming nicotine content, lack of diacetyl (<38 ppm) and acetyl propionyl (<100 ppm). We will purchase the most popular e-liquid from AVAIL at the time of the study and will contain 12 mg/mL.

E-cigarette Device: The study device is a variable wattage all-in-one device, which is inclusive of the three power levels we intend to study. It is important to note that e-

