5.4.4 PARTICIPANT SCHEDULE

Study Arm #1: Power level 10, 15, or 20 watts (computer randomized, single-blinded)	
Hospital Day 1	Hospital Day 2

• Standardized Session• 4-hr abstinence and blood draws• Followed by 90 min Free use session w/ video monitoring	
• Free use• 12-hr CV monitoring• Circadian blood draws• 12-hr urine collection
Study Arm #2: 1 of the other 2 remaining power levels (computer randomized, single-blinded)	
Hospital Day 1	Hospital Day 2

• Standardized Session• 4-hr abstinence and blood draws• Followed by 90 min Free use session w/ video monitoring	
• Free use• 12-hr CV monitoring• Circadian blood draws• 12-hr urine collection
Study Arm #3: Remaining power level (computer randomized, single-blinded)	
Hospital Day 1	Hospital Day 2

• Standardized Session• 4-hr abstinence and blood draws• Followed by 90 min Free use session w/ video monitoring	
• Free use• 12-hr CV monitoring• Circadian blood draws• 12-hr urine collection

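### The printed randomization schedule is a fixed six-row rotation used in booking order, not the computer-randomized order the protocol claims

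*Protocol*

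**What the plan says.** Protocol section 2.4.2 prints 24 numbered orientation rows (headed N = 21), each carrying one of six orders of 10, 15 and 20 W, and then states: "At the orientation visit, the participant will be assigned their treatment sequence from the above randomization schedule". It describes the design as a "counter-balanced randomized treatment order to complete replication with total sample sizes of 21 or 24 (complete Blocks of n= 3"). Rows are used not by order of consent "but rather when he/she is booked for the start of orientation", and the section adds that this timing depends on the availability of the participant, the coordinator and the research unit. The coordinator records the assignment in a tracking log.

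The order is described elsewhere as follows:

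- Section 5.3.1: "The order of the assignment will be randomized, single-blinded".
- Section 5.4.4, for each of the three arms: "computer randomized, single-blinded".

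There is one safeguard in section 2.4.2: "The participant will not be considered for assignment until it has been verified that he/she is eligible and the Eligibility Checklist has been signed". Under section 2.3.3, if nothing triggers referral to the physician, "the CRC and Project Manager will sign off on Eligibility Checklist without Study Physician review".

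On dropouts, section 2.4.2 says that where a block would be incomplete because "a participant has dropped out or been lost to follow up, their orientation assignment can be reused". Further on it says that non-completers are not replaced, that the schedule simply runs on, and that the principal investigator may enrol extra participants.

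**The concern.** The table reads as a cycle, not as the output of a random process. If it is the list actually used, the words randomized and computer randomized describe something the procedure does not do.

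The coordinator, who takes part in the eligibility sign-off and whose own availability helps set the booking date, can also see which order comes next. Who receives which order could then be influenced, deliberately or not, by when orientation is booked. Random order is what supports treating the sequence groups as comparable, and that matters if there is carry-over between arms or if people leave partway through.

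**Working it through.** **Inputs.** The 24 printed rows, the rule for using them and the permitted totals of 21 or 24, all from section 2.4.2. No effect size, standard deviation or dropout rate is needed.

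**1. Pattern.** Row *i* holds sequence ((*i* − 1) mod 6) + 1, and this fits 24 of 24 rows. Sequences 1–3 form one Latin square. Sequences 4, 5 and 6 are sequences 1, 2 and 3 reversed, and form the second square. The order inside the cycle is therefore systematic too.

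**2. The protocol's own balance claim.** It reproduces. Each power level occurs 7 times in each period at 21 and 8 times at 24. The sequences occur 4, 4, 4, 3, 3, 3 times at 21 and 4 times each at 24.

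**3. Could a random draw have produced this table?** No generation method is stated, so two are assumed for illustration.

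- Independent random permutations of six: four identical blocks have probability (1/720)³ ≈ 2.7 × 10⁻⁹.
- Alternating squares with rows permuted in blocks of three: (1/6)⁶ ≈ 2.1 × 10⁻⁵.

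**4. Foreseeability of the printed list.** With the list in hand, 24 of 24 assignments are known. Neighbouring rows always hold different sequences, so exchanging two neighbouring bookings always exchanges the sequences. First-arm powers run 10, 15, 20, 20, 10, 15 and repeat. Only the pairs at rows 3–4, 9–10, 15–16 and 21–22 share a first power, so 23 − 4 = 19 of 23 pairs differ.

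**5. A randomized list that keeps blocks of three.** Within each six, randomize which square comes first and the order of its three rows: 2 × 3! × 3! = 72 possible orders instead of 1. Compare the best guess of someone who remembers every earlier assignment:

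| List | Sequence, correct per 6 | First-arm power, correct per 6 |
|---|---|---|
| Printed rotation | 6 (100%) | 6 (100%) |
| Paired squares | 1/6 + 1/2 + 1 + 1/3 + 1/2 + 1 = 3.5 (58%) | 2 × (1/3 + 1/2 + 1) = 3.67 (61%) |
| Free permutation of six | 1/6 + 1/5 + 1/4 + 1/3 + 1/2 + 1 = 2.45 (41%) | 3.37 (56%) |

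Every block of three in the paired-squares list is a complete Latin square, so period balance is exact at 21 (seven squares) and 24 (eight squares). In 20,000 simulated lists it was never lost. A free permutation keeps balance at 21 only if the last three rows used happen to form a square. Two of the 6!/(3! × 3!) = 20 possible triples do, which is 10%.

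**6. Dropout wording.** Take 21 participants, one dropout and one added participant. Reusing the vacated slot keeps 7 per power per period in 21 of 21 cases. Moving on to row 22 (sequence 4) keeps it only when the dropout also held sequence 4 (rows 4, 10 or 16), so it is lost in 18 of 21. In a linear model with participant, period and power effects, the balanced variance of a pairwise power contrast is 2σ²/21 = 0.0952σ². With row 22 added, the worst contrast's variance rises by a factor of at most 1.0092 (mean 1.0072).

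**The case against.** The strongest reply is that this is a crossover. Each person is their own control, the list is balanced by period, no hypothesis concerns order, and foreseeing the order cannot change who receives a power level. That stands, and it is why the consequence is limited. No bias in the power contrasts is claimed here.

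Second, assignment waits for a signed checklist and takes place with the participant present. The booking date is not the coordinator's alone to set. Sections 2.3 and 8.3 also give the study physician a role in eligibility. These points reduce the scope for steering eligibility. They do not hide the next row, and booking order can still move.

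Third, list generation and concealment are often documented outside the protocol, and a computer-generated list may exist. Silence about concealment alone would be no fault. But section 2.4.2 names the printed table as the source, so if another list is used, that section is wrong. The text needs correcting either way.

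Fourth, paired squares remain fairly guessable, and the last row of each block of three is certain to anyone who has tracked the block. That is true. It is the price of exact balance at 21, and concealment does most of the protective work.

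**Conclusion.** The point holds. As written, the order is a fixed rotation with 24 of 24 assignments foreseeable, and the labels randomized and computer randomized are not supported by the procedure that the protocol itself fixes.

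The harm is confined to that description and to the possibility that booking time shifts who gets which order. Comparisons between power levels are largely protected among completers. The correction should be made, but the design is not undermined. The dropout wording is minor: it leaves two possible slots for an added participant, at a cost in variance of under 1% if period is modelled.

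The conclusion assumes that the printed table is the list in use, as section 2.4.2 says.

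**What to change.** - **Generate the list.** For slots not yet assigned, have a computer choose within each six which square (sequences 1–3 or 4–6) comes first and the order of its three rows.
- **Conceal it.** Keep the list from the coordinator who books visits and reveal only the next assignment at orientation. An existing staff member not involved in booking could hold it. REDCap, already used for screening and data entry, is an alternative if it can be set up for allocation, which the protocol does not say.
- **Or relabel.** If the rotation is kept or has already been used, call it counterbalanced systematic assignment and remove randomized and computer randomized for the order in sections 2.1, 2.4.2, 5.3.1 and 5.4.4.
- **State one dropout rule.** For example, an added participant takes the vacated slot of the incomplete block. This keeps balance, but that single assignment is known in advance. Continuing down the list is also tolerable, given the small loss of precision.

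The cost is a new list for the remaining slots, someone to hold it and one reworded paragraph. Relabelling costs only wording. Visits, sample size and procedures do not change.

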2.5 PARTICIPANT WITHDRAWAL

2.5.1 Dropout Definition

If a participant declares he/she is no longer interested in completing the study, he/she will be considered a "dropout." Once given "dropout" status, the participant can no longer contribute to the study.

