2.5.2 Dropout Compensation

If participant decides to stop participating in the study prior to starting the inpatient portion of the study, he/she will only receive compensation for the Screening Visit (\$30) and no compensation will be given for the inpatient portion.

If a participant decides to drop out during the inpatient study, compensation will be pro-rated for completed visits.

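### Do the reuse and no-replacement sentences in protocol section 2.4.2 leave an added participant's sequence in conflict?

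*Protocol*

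**What the plan says.** Protocol section 2.4.2 (Randomization) prints a 24-row list that cycles through six sequences of 10, 15 and 20 W. The list is headed "Orientation # (N= 21)", and the text plans for "total sample sizes of 21 or 24 (complete Blocks of n= 3)". A participant receives a row at the orientation visit.

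Two passages in that section deal with people who leave:

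- Where a block will be incomplete "because a participant has dropped out or been lost to follow up, their orientation assignment can be reused".
- In the closing paragraph: "If a participant drops out or is lost to follow-up (LTFU) during the study, he/she will not be replaced". It continues: "The assignment schedule will continue as assigned, and the PI can decide to enroll additional participants to compensate for non-completers".

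Section 2.5.1 adds that after dropout "the participant can no longer contribute to the study", so a reused row must go to a different person. Section 2.5.2 separates stopping before the hospital portion from stopping during it, but only for payment. Neither section says anything about rows.

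**The concern.** Both passages have the same trigger: dropout or loss to follow-up after a row has been issued. Giving that row to someone else looks like replacement, which the closing paragraph appears to rule out, while a schedule that carries on as assigned points to the next row. Two coordinators could therefore place the same compensating participant in different sequences.

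The section's own aim is a counter-balanced order in complete blocks. If the choice of row upset that balance enough, power level would be partly confounded with period and the contrasts would lose precision. A choice made by staff after a dropout is known would also be less clean than a rule fixed in advance.

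**Working it through.** **Reading the sentences together.** The reuse sentence is conditional (a block would be incomplete) and permissive (the assignment can be reused). The closing paragraph sets a default: no automatic replacement, and those who follow keep their listed rows. It then lets the investigator add participants to make up for non-completers, so it cannot forbid new people from standing in for those who left. On this reading, an added participant may take a vacated row when that completes a block. What the text leaves out is whether vacated rows must be used before new ones.

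**Inputs.** The printed schedule in section 2.4.2: 1 = 10-15-20, 2 = 15-20-10, 3 = 20-10-15, 4 = 20-15-10, 5 = 10-20-15, 6 = 15-10-20, cycled over 24 rows. Target of 21 completers, as in the table heading. The protocol gives no dropout rate, so k = 1, 2 or 3 dropouts among rows 1 to 21 is assumed, with all patterns equally likely (21, 210 and 1330 patterns). Two practices are compared: *fill* (vacated rows are refilled by completers) and *continue* (rows 22 to 21+k are used).

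**The plan's own figures.** Both 21 and 24 are multiples of the block size of 3. At 21, each power level falls 7 times in each period and sequences 1 to 6 occur 4, 4, 4, 3, 3, 3 times. At 24, each level falls 8 times per period and each sequence occurs 4 times. The stated sample sizes do give complete blocks.

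**Balance, completers only.** Fill restores 7/7/7 in every period for every pattern. Continue adds sequence 4, then 5, then 6, so balance survives in these cases:

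- k = 1: the dropout was on sequence 4, 3 of 21.
- k = 2: one dropout on sequence 4 and one on 5, 3 × 3 = 9 of 210.
- k = 3: one each on 4, 5 and 6, or one each on 1, 2 and 3, 3 × 3 × 3 + 4 × 4 × 4 = 27 + 64 = 91 of 1330.

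Otherwise counts run from 6 to 8 (k = 1) or from 5 to 8 (k = 2, 3). Example: losing row 1 and adding row 22 gives 6/7/8 for 10/15/20 W in period 1, 7/7/7 in period 2 and 8/7/6 in period 3.

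**Precision, completers only.** In a least-squares model with participant and period effects, a balanced set of 21 gives each contrast a variance of 2/21 = 0.0952 in units of within-person variance. Averaged over the three contrasts and all patterns:

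| k | Fill | Continue | Mean increase | Largest increase, single contrast |
|---|---|---|---|---|
| 1 | 0.09524 | 0.09567 | 0.46% | 0.9% |
| 2 | 0.09524 | 0.09587 | 0.67% | 2.1% |
| 3 | 0.09524 | 0.09583 | 0.62% | 2.1% |

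For k = 1 the largest increase is 0.68% if the three contrasts are averaged first. On the standard-error scale, the largest mean increase is √1.0067 − 1 = 0.3% and the worst case is √1.021 − 1 = 1.0%.

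**If dropouts' partial data are kept.** A dropout with one period adds nothing to a within-person contrast, so the variances are the same as in the table. With two periods contributed, the excess under continue is 0.23%, 0.24% and 0.06% for k = 1, 2, 3. Exact balance is then not guaranteed by either practice. With three dropouts contributing two periods each, equal counts in every period occur in 91 of 1330 patterns under fill and 343 of 1330 under continue.

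**Order effects.** At 21 the direct transitions are uneven even with no dropouts: 8 each for 10→15, 15→20 and 20→10, and 6 each for the reverse steps. In the example above, continue takes 10→15 and 15→20 from 8 to 7 and raises 20→15 and 15→10 from 6 to 7. It gives up a little period balance and evens out the transitions slightly, so filling is not better on every count.

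**The case for a change.** The best case for acting is that the fault lies in the text, whatever the lost precision. This is an allocation instruction in the protocol itself, so it is not something an analysis plan would normally supply. A coordinator reading it cannot tell which row an added participant receives, and the rows numbered 22 to 24 in a table headed 21 add to the doubt. The reading that reconciles the sentences is not written down, nor is a split between loss before and loss during the hospital portion. One sentence would fix the sequence by rule, with no extra enrolment and no loss of the investigator's discretion.

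Most of this stands as a remark on drafting: the wording is loose, and a sentence naming the row would be harmless. It does not show a contradiction, because a permission for a stated purpose can sit beside a default that itself allows compensating enrolment. Nor does it show a material gain. A mandatory vacated-rows-first rule is one reasonable preference: it keeps period balance exactly only among completers, and it does nothing for the uneven sequence counts at 21. Rows 22 to 24 also have an ordinary explanation, since the section allows a total of 24.

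**Conclusion.** No change follows. Section 2.4.2 leaves one operational detail unwritten, the row given to a participant enrolled to make up for a non-completer, and staff can settle it sensibly either way. Among completers the choice may shift power-by-period counts from 7 to between 5 and 8. The mean cost in contrast variance is below 1% and the worst case is 2.1%, both removed of confounding once period is in the model. No bias is shown: each participant is scheduled for all three power levels, and either practice takes the sequence from the printed list.

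This rests on one to three dropouts, equally likely patterns, a target of 21 completers, and an analysis with participant and period effects. The first three are assumptions beyond what the protocol fixes. A larger number of dropouts was not examined.
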